2.3.2.1 PRIMARY ENDPOINT ANALYSIS

To test these hypotheses, the difference in the proportions of responders and a 95% Confidence Interval (CI) of the difference in proportion of responders will be calculated using the normal approximation to the binomial distribution. Non-inferiority will be claimed if the lower limit of

the 95% CI is greater than -5%. Furthermore, superiority will be claimed if the lower limit of the 95% CI is greater than 0%. The p-value for superiority will also be reported, based on a Chi-Square test. The total number of successes in each study arm will be summarized, along with the corresponding proportions and exact 95% CIs.

The ITT population will serve as the primary analysis population. For this analysis, if a subject does not complete the 12 week assessment, their outcome will be imputed using multiple imputations (Schafer, 1997). The multiple imputation methodology will be implemented as follows:

1. Ten imputed datasets will be generated to impute missing urine leakage using the below SAS code. Only the imputed values at Week 12 will be retained.

```
Proc MI NIMPUTE=10 SEED=20150930 MIN=0 0 0 MAX= . . .;  
  var base w4 w12;  
  fcs reg(base) reg(w4) reg(w12);  
run;
```

2. The ten imputed datasets will be analyzed separately. Using the methodology described above, the Week 12 urine leakage will be compared against the baseline weights to classify subject responders.
3. The proportion of responders in each treatment group, along with the associated standard error, will be calculated for each of the ten imputed datasets. The individual proportion estimates and standard errors will be pooled by treatment using the SAS code below.

```
Proc MIANALYZE;  
  modeleffects prop;  
  stderr se_prop;  
  by trt;  
run;
```

4. The difference in the proportions of responders and the standard error of the difference will be calculated for each of the ten imputed datasets. The individual estimates of the difference in proportions, as well as the associated standard errors of the differences, will be pooled using the SAS code below.

```
Proc MIANALYZE;  
  modeleffects prop_diff;  
  stderr se_diff;  
run;
```

A supportive analysis will also be conducted using similar methodology in the PP population.

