1.4 SAMPLE SIZE AND POWER

Sample size calculations were performed using the NQuery Advisor® version 5.0, under a two group test of proportions.

Research suggests that the response rates for Vital Compact and itouch Sure at 12 weeks will be 71% and 46%, respectively (itouch success rate based on Sand, 1995).

The sample size calculation is based on the assumption that the itouch Sure Pelvic Floor Exerciser success rate is 52% and the Vital Control success rate is 71%. A sample size of 87 subjects per group will provide 90% power using a one-sided Type I error rate of 0.025, and a non-inferiority margin of 5%. A randomization allocation of 1:1 was also assumed. For practical reasons, the sample size has been increased to a recruitment of 180 subjects (90 subjects per treatment group).

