2.3.2 PRIMARY ENDPOINT HYPOTHESIS

The primary hypothesis is that the proportion of subjects who respond (i.e. have achieved ‘significant improvement’) using Vital Compact is not less than 5% worse than the itouch Sure Pelvic Floor Exerciser (i.e. the lower bound of the confidence interval about the difference between device groups should be greater than -5%):

$$H_0: p_{Vital\ Compact} - p_{control} \leq -5\%$$

$$H_1: p_{Vital\ Compact} - p_{control} > -5\%$$

where $p_{Vital\ Compact}$ is the proportion of subjects who respond with Vital Compact and $p_{control}$ is the proportion of subjects who respond with itouch Sure Pelvic Floor Exerciser.

If the primary hypothesis of non-inferiority is met, a hierarchically-nested test of superiority will be performed. The hypothesis for the assessment of superiority is:

$$H_0: p_{Vital\ Compact} - p_{control} \leq 0\%$$

$$H_1: p_{Vital\ Compact} - p_{control} > 0\%$$

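### Ten imputations leave a small, avoidable simulation error in the primary lower confidence limit; 100 or more would remove most of it at almost no cost

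*SAP*

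**What the plan says.** SAP 2.3.2.1 imputes missing Week 12 leakage by multiple imputation: "Ten imputed datasets will be generated to impute missing urine leakage using the below SAS code". The code line is "Proc MI NIMPUTE=10 SEED=20150930", with regression imputation on baseline, Week 4 and Week 12 leakage. Each imputed Week 12 value is then classified as responder or non-responder. The arm proportions and their difference are pooled with PROC MIANALYZE.

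The claim rests on one number. Non-inferiority is declared if the lower limit of "the 95% CI is greater than -5" percent, and superiority if that limit exceeds 0%. SAP 2.3.2 words the hypothesis the same way: "the lower bound of the confidence interval about the difference between device groups should be greater than -5" percent. SAP 1.4 sizes the trial "using a one-sided Type I error rate of 0.025" "and a non-inferiority margin of 5" percentage points.

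The same section adds: "The p-value for superiority will also be reported, based on a Chi-Square test". It also asks for the count of successes and exact 95% intervals in each arm.

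The SAP gives no reason for ten imputations, no target for Monte Carlo error and no rule for raising the number. SAP 2.5 uses multiple imputation in the futility analysis without stating a number.

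**The concern.** Ten imputations are ample for efficiency: with 10-20% missing information, relative efficiency is 1/(1 + 0.1/10) = 0.99 to 1/(1 + 0.2/10) = 0.98. Repeatability of a pass/fail decision is a different matter. The endpoint dichotomises each imputed value, so the responder count changes from draw to draw, and an average over ten draws still carries some of that variation. If the pooled limit falls very close to -5% or 0%, another equally legitimate seed could give the other answer. The primary result also gates the superiority test and the eleven key secondary endpoints (SAP 2.3.3).

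A second, smaller matter is that ten completed datasets yield ten chi-square tests, ten success counts and ten pairs of exact intervals. The code pools only the proportions and their difference, and the SAP does not say how the other outputs are to be combined.

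**Working it through.** **Inputs.** From SAP 1.4: 71% and 52% response, 5-point margin, one-sided 0.025, 87 per group raised to 90. From SAP 2.3.2.1: M = 10 imputations. The proportion missing at Week 12 appears in neither document; 5% to 30% per arm is assumed below.

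**The plan's own figure.** Shift the control rate by the margin, 52% - 5% = 47%, and apply the two-proportion formula to 47% and 71% (mean 59%):

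n = [1.960 x sqrt(2 x 0.59 x 0.41) + 1.282 x sqrt(0.47 x 0.53 + 0.71 x 0.29)]^2 / 0.24^2 = 86.2, so 87 per group. The inputs reproduce the stated size.

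**Sampling error.** v = 0.71 x 0.29 + 0.52 x 0.48 = 0.4555. With 90 per arm, SE = sqrt(0.4555/90) = 7.11 points. The expected lower limit is 19 - 1.96 x 7.11 = +5.1%, about ten points above -5%.

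**Monte Carlo error.** If a fraction f of each arm is imputed, and baseline and Week 4 are uninformative:

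- Between-imputation variance of the difference: B = f x v/90.
- Noise in the pooled difference: sqrt(B/M).
- Noise from the estimated standard error: 1.96 x (1 + 1/M) x B x sqrt(2/(M-1)) / (2 x sqrt(T)), where T = v/90 + (1 + 1/M)B.
- The two are combined as a root sum of squares.

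At f = 10%: B = 0.1 x 0.4555/90 = 0.000506. The first part is sqrt(0.0000506) = 0.71 points. T = 0.00562, and the second part is 0.34 points. Together, sqrt(0.71^2 + 0.34^2) = 0.79 points.

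Simulations of the coded procedure, holding the data fixed and varying the seed, check this. They need assumed leakage distributions (for example, baseline lognormal with median 15 g, restricted to the 3-90 g entry range), so they are approximate. All SDs are in percentage points, for M = 10:

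| Missing per arm | Pooled difference, analytic | Lower limit, analytic | Lower limit, simulated |
|---|---|---|---|
| 0% | 0 | 0 | 0 (by definition) |
| 5% | 0.50 | 0.53 | 0.41-0.46 |
| 10% | 0.71 | 0.79 | 0.67-0.70 |
| 15% | 0.87 | 1.01 | 0.8-0.9 |
| 20% | 1.01 | 1.20 | 0.9-1.0 |
| 30% | 1.23 | 1.55 | 1.27-1.32 |

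With M = 100, the SD of the lower limit at 10% and 20% missing is 0.24 and 0.37 (analytic), or 0.21 and 0.29 (simulated).

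**Effect on the decision.** Let the noise-free limit L be normal with the expected limit as mean and the sampling SE as SD, and let s be the Monte Carlo SD. Two seeds disagree about threshold c with probability E[2 x P x (1 - P)], where P = Phi((L - c)/s). For s = 0.7 and 1.0 points:

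- 71% and 52%, threshold -5%: 1.6% and 2.4% of trials.
- 60% and 52% (SE 7.4, expected limit -6.5%), threshold -5%: 4.2% and 5.9%.
- 71% and 52%, threshold 0%: 3.4% and 4.9%, since the expected limit of +5.1% is nearer to 0%.

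With s = 0.2 to 0.3, as at M = 100, the first figure falls to about 0.5-0.7%.

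**Interim.** With about 45 per arm, ten imputations would give a Monte Carlo SD of the difference of sqrt(0.1 x 0.4555/45/10) = 1.0 point at 10% missing, and 1.4 points at 20%.

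**The case against.** The case against making much of this is strong, and most of it stands.

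- **Missingness may be low.** Subjects who stop early are asked back for a Visit 4 assessment (Protocol 8.11.1), which is recorded as Week 12 (SAP 1.6.2). Randomised subjects who never use the device leave the analysis set under the mITT rule (SAP 2.1). A rate of 5% or less is as plausible as 20%. A reader might take 0.7-1.0 points as a property of the plan, but it holds only at about 10-20% missing.
- **The interval is not invalid.** A reader might infer lost coverage or an inflated type I error. Rubin's variance includes the (1 + 1/M)B term with a t reference, so the finite number of imputations is already counted.
- **The seed is prespecified.** A reader might infer that the result is irreproducible or that a seed could be chosen afterwards. Rerunning the planned code returns the planned result. The limit to this is that seeded draws also depend on software and record order; SAP 1.6.4 allows later SAS versions or another package, and the record order is not specified.
- **The 5-point margin is the wrong yardstick.** Against the 7.1-point sampling SE, noise of 0.7-1.0 points is (0.7/7.1)^2 = 1% to (1.0/7.1)^2 = 2% of the variance.
- **Sensitivity analyses exist.** LOCF and the tipping-point grid (SAP 2.3.2.2) have no simulation noise, and the grid examines dependence on imputed outcomes more broadly. Neither is the decision rule, so neither removes the noise from the primary limit.
- **The chi-square p-value is an additional report.** Both claims rest on the confidence limit, so the missing combination rule affects presentation, not the claim.

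What survives is that the noise says nothing about the devices and can be removed at almost no cost.

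**Conclusion.** This is a minor, avoidable imprecision and not an error in the analysis. The primary lower limit varies across seeds with an SD of about 0.4-0.5 points at 5% missing, 0.7 at 10% and 1.0 at 20%. It matters only if the limit falls within about 1-2 points of -5% or 0%. At the planning rates the seed would change the non-inferiority conclusion in about 2% of trials. To say that the seed and not the data decides the trial would go beyond what the documents support.

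The figures assume 90 per arm, equal missing rates in the two arms and the leakage distributions used in the simulation. The missing rate is the main unknown. The decision frequencies use s = 0.7-1.0 points, which corresponds to 10-20% missing. The content of the imputation model is a separate question and is not judged here.

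**What to change.** In SAP 2.3.2.1, before unblinding:

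1. Set NIMPUTE to at least 100 and keep the prespecified seed. State the record order before imputation.
2. Report the Monte Carlo error of the pooled lower limit beside the limit.
3. For the multiply imputed analysis, take the superiority p-value and the arm-level intervals from the pooled PROC MIANALYZE output, so that they agree with the confidence-limit rule. Keep the chi-square test and exact intervals for analyses with a single dataset: LOCF, and the per-protocol set, which requires an observed Week 12 outcome.
4. State the same number of imputations for the futility run in SAP 2.5. The gain there is smaller in consequence, because that rule is advisory.

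The cost is one changed number, a few lines of text and a little computing time. The endpoint, margin, imputation model and decision rule are unchanged.

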Castro (2008) reported a significant decrease in urine lost during pad tests and in the number of stress urinary episodes, as well as a significant improvement in the quality of life, in subjects who underwent a programme of pelvic floor exercises, electrical stimulation or use of vaginal weights compared to a control group. In this study there was no observed difference between treatment groups suggesting each intervention to be equally effective. While it is reported that these interventions can be effective in the treatment of stress urinary incontinence the issues of technique, comfort of treatment and compliance with treatment are often limiting factors that impact patient outcomes. This has motivated the search to identify an electrical stimulation treatment modality that ensures satisfactory recruitment of the pelvic floor muscles and that is easy to administer and more comfortable for the patient. This resulted in the development of a novel electrical stimulation (ES) device that includes a wired garment which locates a set of skin contact electrodes around the pelvic area.

A pilot study (n=9) with this novel ES system (first generation device called UCD RS device) conducted at University College Dublin has shown improved outcomes (Maher and Crowe, 2008) following an 8 week treatment programme. In particular, subjects using the ES system achieved a significant decrease in symptoms when compared to the control group. At Week 1 all subjects could perform appropriate volitional contractions of their pelvic floor muscle in standing but more importantly there was a reported 87.43% decrease in leakage. At Week 8, subjects reported a 97.71% decrease in leakage ($P<0.01$) and the IIQ-7 and Modified Oxford scores also changed significantly ($P<0.01$).

A pilot study (n=19) has recently been completed in Germany at St. Hedwig Krankenhaus (Soeder and Tunn, 2013) which looked at a 12 week treatment programme with the second generation device (called Inko RS device). Sixteen subjects completed baseline measurements while 14 and 13 subjects completed the 12-week and 26-week assessments, respectively. Mean (SD) urine leakage on the 1-hour and 24-hour pad weight tests improved ($p<0.05$) from 41.6g (43.92) to 5.8g (13.19) and 21.8g (19.41) to 5.6g (5.16) respectively after completion of the 12 week programme. These improvements were substantially retained at the 26 week point. In

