6.2 Inclusion Criteria

1. Subjects who are female and at least 18 years of age, and not more than 65 years of age.
2. Subjects who have signed the informed consent form prior to any study related activity.
3. Subjects who have previously tried and failed to improve their condition using Kegel exercises.
4. Subjects who have been clinically diagnosed with stress urinary incontinence and demonstrate a greater than or equal to 3g urine leakage and a less than or equal to 90g urine leakage ($\geq 3g$ and $\leq 90g$) following a bladder-filling protocol and then a standardised stress test (provocative pad weight test) at the baseline assessment.
5. Subjects who score 9 or less (≤ 9) out of 18 for the Urge Incontinence Questions and are confirmed as having predominant stress urinary incontinence on the Medical, Epidemiologic and Social Aspects of Aging Urinary Incontinence (MESA) Questionnaire completed at the screening assessment.
6. Subjects with a Body Mass Index of $\leq 35 \text{ kg/m}^2$.
7. Subjects of child-bearing potential who are using a highly effective contraceptive method (established use of oral, injected, implanted hormonal method of contraception or barrier method of contraception with spermicide).
8. Subjects who are willing not to seek any other treatment for stress incontinence during the study period.
9. Subjects who are able to give voluntary, written informed consent to participate in this study and from whom consent has been obtained.
10. Subjects who are able to understand this study and are willing to complete all the study assessments.

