6.4 Withdrawal Criteria

During the course of this study, subjects may be withdrawn, or may elect to withdraw through any of the listed following reasons below. However all subjects will be assessed on an individual basis when clarifying their withdrawal and for this reason, measurable parameters cannot be specifically defined for the withdrawal criteria below:

- Subject's rescission of consent.
- Any adverse event, related to the device or not, which may endanger the well-being of the subject if they were not withdrawn.
- Subject non-compliance or protocol violation.
- Subject unable to meet the protocol requirements.
- Development of a medical condition or illness which may compromise safety of the subjects or invalidate the results of the study.

The Investigator will clearly document the date and reason(s) for withdrawal in the Case Report Form.

All subjects discontinued from the study due to an adverse event will be followed up by the Investigator until resolution or condition has stabilised.

Subjects who are withdrawn prior to the completion of the baseline assessments only will be replaced.

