7.5 Randomisation and Blinding

Subjects will be randomised to the Neurotech Vital Compact device or the itouch Sure Pelvic Floor Exerciser (1:1 ratio). They will know to which device they have been randomised since the two devices will be described in detail in the patient information sheet i.e., the Neurotech Vital Compact device delivers electrical stimulation through external electrodes and the itouch Sure Pelvic Floor Exerciser delivers electrical stimulation through an internal vaginal probe.

The site personnel who perform the device training at baseline and monitor the device compliance at the follow-up visits will not be blinded, but the personnel who perform the follow-up assessments will be blinded regarding device assignment.

Verification to ensure that this blinding is maintained will be assessed at the monitoring visits.

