8.10.1 Device Training

Subjects will be briefed by the designated non-blinded site personnel on the set-up of the Neurotech Vital Compact device or the itouch Sure Pelvic Floor Exerciser (in accordance with the allocated treatment as per the randomisation schedule). Subjects will then be asked to follow

the set-up instructions and complete a 30 minute session with the Neurotech Vital Compact device or a 20 minute sessions with the itouch Sure Pelvic Floor Exerciser in accordance with the appropriate Instructions for Use. Subjects will be at liberty to alter the intensity of the stimulation to the highest tolerable level and will be advised on the importance of achieving a strong pelvic floor contraction. Guidance will be given on the typical minimum intensity setting to achieve this effect. Subjects will be advised that it not necessary to achieve this level in their first session but that they should gradually increase the setting in their first week of use.

All of the subject's training will be documented. Subjects unable to demonstrate competent use of the Neurotech Vital Compact device or the itouch Sure Pelvic Floor Exerciser will be withdrawn from the clinical study.

The subject will be provided with the Neurotech Vital Compact device or the itouch Sure Pelvic Floor Exerciser to take home with them. Details of all devices provided, including the serial/lot numbers, will be recorded.

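### The primary-analysis imputation uses zero-bounded normal regression on raw grams with no treatment term, which distorts the device difference if data are missing at random within arm

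*SAP*

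**What the plan says.** SAP 2.3.2.1 makes the ITT comparison with multiple imputation the primary analysis. The imputation step lists three variables, "var base w4 w12", and models each by linear regression, "fcs reg(base) reg(w4) reg(w12", in grams with a lower limit of 0 and no upper limit. That step has no treatment variable, BY statement or transformation; treatment first appears when results are pooled. Imputed grams are then compared with baseline, and a drop of more than half counts as response. Non-inferiority needs the lower 95% limit to exceed −5 points.

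Protocol 10.3.4 says only that multiple imputation will be used. Neither it nor SAP section 4 states what is assumed about missing women. SAP 2.5 also uses multiple imputation for the futility calculation. SAP 2.3.2.2 adds LOCF and a tipping-point grid. SAP 1.6.2 stores early-termination visits as Week 12, and SAP 2.1 removes never-users through an mITT population.

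On the data themselves, women must "demonstrate a greater than or equal to 3g urine leakage and a less than or equal to 90g urine leakage" at baseline (Protocol 6.2). The pilot of an earlier external-electrode device (Protocol 2.1) reports mean (SD) leakage on the 1-hour test "from 41.6g (43.92) to 5.8g (13.19" g), and "Sixteen subjects completed baseline measurements while 14 and 13 subjects completed the 12-week and 26-week assessments, respectively".

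**The concern.** The endpoint compares arms on a ratio to baseline, but the imputation model knows neither the arm nor the ratio. Two separate effects follow.

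- **Scale and floor.** Leakage is skewed. A normal error of one size in grams, with negative draws excluded, pushes many low-baseline women above their responder cut-off.
- **No arm.** Women with the same baseline and Week 4 values get the same imputation model whichever device they used.

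The result of this analysis gates the superiority test (SAP 2.3.2) and all 11 key secondary tests (SAP 2.3.3), and the same method feeds the 30% conditional-power threshold at the interim. An unstated assumption about missing women therefore enters the trial's main claim.

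**Working it through.** **1. The plan's own figure.** With rates of 71% and 52%, margin 5 points, one-sided 0.025 and 90% power (SAP 1.4), mean rate 0.615:

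n = 2 × 0.615 × 0.385 × (1.960 + 1.282)² / (0.71 − 0.52 + 0.05)² = 86.4, so 87 per group.

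This matches the SAP. The calculation contains no allowance for missing data beyond rounding up to 90.

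**2. Why the imputed share is low.** Entry at 3–90 g puts the responder cut-off at 1.5–45 g. In the pilot the Week 12 SD is 13.19/5.8 = 2.3 times the mean. As an illustration that ignores the regression on baseline, a normal with that mean and SD has Φ(−5.8/13.19) = Φ(−0.44) = 33% of its mass below 0. Redrawing those values above 0 raises the mean from 5.8 g to 5.8 + 13.19 × 0.362/0.670 = 12.9 g.

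**3. What the share does to the difference.** With missing fraction m, true rate p and imputed share s, an arm's estimate is (1 − m)p + ms when missingness is unrelated to outcome.

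- *71%/52%, 12.5% missing in each arm* (the pilot's loss, 2/16). Simulated shares were 27%/26%: (0.875 × 0.71 + 0.125 × 0.27) − (0.875 × 0.52 + 0.125 × 0.26) = 0.655 − 0.4875 = +16.75 points. If the shares are equal the result is 0.875 × 19 = +16.6 whatever their level. With shares of 53%/41% (Week 4 observed and strongly predictive) it is 0.6875 − 0.5063 = +18.1.
- *47%/52%, 5%/20% missing* (Vital Compact/control). With a common share s: (0.4465 + 0.05s) − (0.416 + 0.20s) = 0.0305 − 0.15s. For s of 8%, 26% and 36% this gives +1.9, −0.9 and −2.4 points against a true −5.

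**4. Simulation.** All inputs below are assumptions: 90 per arm; baseline log-normal (median 15 g, log SD 0.8) truncated to 3–90 g; log ratio to baseline SD 0.9 (range 0.7–1.4), or a bounded ratio (uniform 0–0.5 for responders, 0.5–1.1 for others); Week 4/Week 12 correlation 0.6, with Week 4 carrying half the effect; half of the women missing Week 12 also missing Week 4; 10 imputations; Rubin's rules; missingness unrelated to outcome within arm. Most cells used 3,000–4,000 trials, some checks fewer.

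| True rates | Missing | SAP code | Log scale, by arm |
|---|---|---|---|
| 71%/52% | 5%/5% | power 89% | 91% |
| 71%/52% | 12.5%/12.5% | +16.5 to +16.7; power 82–84% | about +19; 87–89% |
| 71%/52% | 20%/20% | power 76% | 87% |
| 71%/52% | 10%/5% | power 81% | 91% |
| 71%/52% | 20%/5% | power 47–70% | 88–89% |
| 47%/52% | balanced | false NI 2.2–2.7% | 2.2–2.7% |
| 47%/52% | 5%/10% | false NI 2.5–3.8% | 2.0–2.3% |
| 47%/52% | 5%/20% | false NI 6–13% log-normal; 3.4% bounded | 1.4–2.7% |

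With Week 4 observed and strongly predictive, the 5%/20% figure falls to 3.2–3.5%. One smaller run with a wider spread (log SD 1.2, 500 trials, standard error about 1.2 points) gave 8.2% against 1.4% at 10%/20%.

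**5. Which part does what.** Removing the floor raises the shares in the main setting from 27%/26% to 47%/46%, so the floor is the main cause of the low level. A log model that still omits arm gives +17.1 points and 85% power at 12.5% balanced loss, so omitting arm drives the balanced-loss cost. Adding arm but keeping bounded grams still gives false non-inferiority of 8.3% at 5%/20% (9.4% without arm in the same run). Both parts need changing.

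**6. Informative dropout.** Hold the overall rates fixed and let only 20% of missing women respond, at a true −5:

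- 5%/20% missing: SAP code 2.0% (mean −4.9), arm-specific log model 0.5% (mean −10.1).
- 20%/5% missing: SAP code 2.0% (mean −5.2), arm-specific log model 6.8% (mean −1.2); matching by arm 7.3%.
- Balanced 12.5% at 71%/52%, 20–40% responding: SAP code +19, arm-specific log model +21.

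**The case against.** Four points weigh on the other side.

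- **Week 4 is in the model.** Where it is observed and predictive it carries arm information, and the shares are neither equal nor very low. A reader might infer that the code gives every missing woman the same low chance whatever her device; that is too strong. This stands and limits the size of the effect.
- **Error inflation needs unequal loss.** A reader might infer that the vaginal-probe arm will lose more women, so that the code favours the new device. The documents do not support that. The only retention figure is a 16-woman pilot of an earlier external-electrode device, and "the two devices will be described in detail in the patient information sheet", so women know both routes before randomisation. Balanced loss does not inflate false non-inferiority.
- **The replacement is not always better.** Women leave for reasons such as "Subject non-compliance or protocol violation", and "Subjects unable to demonstrate competent use of the Neurotech Vital Compact device" or the comparator are withdrawn. Such women may be mostly non-responders, and step 6 shows the existing code can then be closer to the truth. This stands: missing at random within arm is an assumption, not a fact.
- **Mitigation is planned.** Early-termination visits stored as Week 12 and the mITT rule reduce what is imputed, and the tipping-point grid does not use the imputation model. But the grid shows dependence on the missing outcomes; it does not change the estimate on which the claim rests.

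**Conclusion.** The point holds and should be fixed, with medium confidence in its size. The model omits arm and uses bounded normal grams. Under missing at random within arm, that costs about 2.5 points of the difference and roughly 5 points of power at an assumed 12.5% balanced loss. At a true −5 points and an assumed 5%/20% loss it gives false non-inferiority of about 3–13%, depending on skew and on how predictive Week 4 is. At 5%/10% or balanced loss the error rate changes little.

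Two stronger conclusions are tempting. One is that the plan as written inflates the type I error; that needs a dropout imbalance the documents neither state nor imply. The other is that a low imputed share is safely conservative; under unequal loss it penalises whichever arm loses more data, so it can favour either device. What the documents do show is that the primary analysis carries an assumption about missing women that comes from the shape of the leakage data and not from a stated rationale. Every dropout rate and distribution used here is assumed.

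**What to change.** Before unblinding:

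1. Run the imputation `BY trt`, or include `trt` in the imputation models.
2. Replace `reg` with `MIN=0` on grams by predictive mean matching, or by a log-scale model without the gram bound. Adding arm alone does not repair the problem. Matching is preferable if many women record 0 g. At 5%/20% loss and a true −5, a log(x + 0.1) model gave mean differences of −6.9 (40% of responders at 0 g) and −6.3 (bounded data); matching by arm gave −5.8 and −5.6, with false non-inferiority of 1.7% and 1.8%. Neither is exact.
3. State that the primary analysis assumes missing at random within arm, and interpret it alongside the planned tipping-point grid.
4. Use the same model in the interim futility calculation (SAP 2.5).

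The cost is a few lines of SAP code and one sentence, with no new data. The downside is that the new model can itself err if dropout is informative; the tipping-point grid will show how far the conclusion depends on that.
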